10.2.3.2 New IVR Participant

Before crossing over participants to the IVR, the participant will need to have the RheumPRO app uninstalled from their smart phone. To uninstall app: hold down on the desired app to uninstall. Once the app begins to shake, tap the x in the top left corner to delete the app from the phone

- First uninstall the RheumPRO app by holding down on the app until it starts to wiggle. Tap the "X" in the top left corner and confirm deletion.

- After uninstalling of RheumPRO app, patient will need to log-on to website to register with IVR system
- Website to log-in: secure.aging.uab.edu
 - Password: **[name]**

Division of Gerontology, Geriatrics, and Palliative Care Logon Page

[figure not shown]
This page is used to access documents.

Palliative Care Resident Library

Study of Aging

Gout Pro Study

- Once password has been entered on website, please have the following information ready
 - Study ID
 - Patient preferred phone number
 - Preferred Call Time

This page is for data entry. 

Subject ID:
Subject phone number:
Preferred call time (Format military time HH:MM):

- Immediately after entering information into webpage a call will need to be placed to IVR system
 - **[contact])**
- Enter study ID using keypad into IVR
- Record patients name, using their own voice and complete first flare assessment using touch-tone keypad on smart phone
- Make sure the coordinator writes down the preferred call time for IVR system and preferred phone number for future calls
- Remind participant of IVR call schedule.
 - Will be conducted weekly throughout the study period
 - Participant will designate a time for phone calls to be made
 - Confirm preferred phone number for IVR calls

- Provide participant with reminder card and trouble-shooting pamphlet
 - Card will have study ID and phone number
 - Remind participant that study ID will be entered into IVR to confirm participation
- At the end of the visit, the coordinator will need to send enrollment form, consent form, W9, and preferred phone number, and call time to UAB
 - Send all forms the same day to [contact]

10.2.4 Visits 14-26

- Phone IVR/RheumPRO Visit by patient
- Participants will receive notification the day of, 24 hours, and 48 hours later
 - IVR will call at designated intervals to complete
 - RheumPRO will send push notification to complete survey

10.2.5 Unscheduled Visit (IVR/RheumPRO report initiated by patient)

In the event a participant experiences multiple flares in a single week participants have the ability to enter flare information on an ad hoc basis.

- IVR: [contact]
 - Call into the system, enter study ID and begin assessment
- RheumPRO
 - Log into RheumPRO (open app) tap to complete flare assessment to being survey

10.2.5.1 RheumPRO Participant

- In the event that the participant has a gout flare in-between the scheduled weekly surveys the participant can open the RheumPRO app and complete a survey
 - Describe the process of opening the app and finding the interval gout flare assessment survey icon to the participant
 - Stress to them the importance of completing this form ONLY when they feel they are having a gout flare

10.2.5.2 IVR Participant

- In the event the participant has a gout flare in-between the scheduled weekly surveys, the participant can make an unscheduled call to the IVR system to report their flare
 - Review the process for completing the flare assessment via the IVR
 - The phone number and study ID can be found on the reminder card
 - The IVR phone number to call is **[contact]**
 - The will need to enter their study ID using the touch tone key pad and then they will be able to complete the flare assessment

11 Data Collection, Study Forms, and Logs

All data for this study will be collected by study staff in accordance with 21 CFR Part 11 rules and will meet all regulatory requirements.

11.1 Study Participant Forms

Data will be collected by the study staff at each visit on study forms as described and presented below:

Form	Description	Visit administered	Instructions	Location
Informed consent	Informed consent	Visit 1	Participant reads through consent and initials each page in the box. Participant, doctor obtaining consent and study staff should all sign, date and time stamp	Tab 2.2 Study Binder
Paper Screening (Patient)	Ensures eligibility by determining that all inclusion criteria are met.	Pre-visit Phone call	Completed by study staff via phone call preceding initial exam. Certified by study coordinator.	Tab 2.3 Study Binder
Paper Screening (Physician/Staff)	Quick sheet to ensure eligibility by determining that all inclusion criteria are met	Visit 1	Completed by study staff prior to initial exam	Tab 2.4 Study Binder
Paper Enrollment	Detailed contact sheet for participant and one other listed contact	Visit 1	Participant is asked for contact information for his/herself and one other person	Tab 2.5 Study Binder
W9 Form for Patient Honoraria	W9	Visit 1	Completed by patient to receive study payment	Tab 2.6 Study Binder
FAQ Sheets	FAQ Sheets for IVR and RheumPRO	Visit 1 and 13	Participant FAQ sheets to help with any unanswered questions	Tab 2.7 Study Binder

11.2 Study Specific Administrative Forms, Logs, and Data Tables

Form	Description	Location
Schedule of Visits and Evaluations	Listing of all schedule study visits and evaluations	Tab 4.1 Study Binder
Training log	Record of trained study personnel	Tab 4.2 Study Binder

Screening log	Log of individuals screened and enrolled	Tab 4.3 Study Binder
Telephone Contact Log	Record of all calls between study staff and participants. Study coordinator(s) complete log showing interval visit calls.	Tab 4.4 Study Binder
Protocol deviation log	A record of all of the protocol deviations that occur throughout the study. It contains explicit instructions for recording the incident and should be updated each time a deviation occurs.	Tab 4.5 Study Binder
Study Completion form	Record of participant study completion/withdrawal	Tab 4.6 Study Binder
Paper Screening (Patient) Phone Script	Phone Script for Paper Screening call to determine eligibility and potential update of labs prior to clinic visit	Tab 4.7 Study Binder

12 Data Management

Data management will be the responsibility of the research assistants, study coordinator, project manager and study statistician. The study statistician will oversee the data management, training coordinators to ensure proper data entry, editing and updating will be the responsibility of the research assistants, while tracking and corrections will be the responsibility of the entire staff. All data will be exported into SAS files and stored on a secure and encrypted server or hard drive. From these data sets, logic among the variables and out of range checks will be conducted every 2 weeks. The study statistician will develop validity checks for outlier values, consistency, and completeness and will notify the principal investigator if issues are identified. Discrepancies will be adjudicated by consultation with the principal investigators. Once data entry is complete, the study data will be transferred to SAS statistical software and reviewed by the statistician. All efforts will be made to ensure the data is in compliance with the UAB Institutional Review Board (IRB) policies, Good Clinical Practice (GCP) guidelines, and Federal regulations.

12.1 Data Entry

Data collected by RheumPRO and IVR will be downloaded from IVR and RheumPRO databases and entered into an excel spreadsheet. Data from screening and enrollment paper forms will be entered directly into the excel spreadsheet by the UAB Study Coordinator. Data entered into the system will be downloaded every two weeks and the database will have range and validity checks built in.

12.1.1 General Instructions for Completing Paper Forms

All data will be maintained according to FDA and ICH Good Clinical Practice (GCP) guidelines. Instructions for completing Case Report Forms (CRFs) to ensure quality and consistency in data collection are below.

12.1.2 Sample instructions

When completing paper study forms participants must not be identified by name on any study document submitted with the forms. Replace the participant name with the participant initials and identification (ID) number.

12.1.3 Header

Complete the header information in every field, including fields for which no study data are recorded. From the drop down box choose Not Applicable, Unknown, or UNK for fields where no data can be provided.

12.1.4 Study ID

The Study ID will be prepopulated in the header of the screening and enrollment pages

12.1.5 Dates

All dates will be verified by the study coordinator. Historical dates are sometimes not known (e.g., date of first symptom); in this case, chose Not Applicable, UNKNOWN or UNK to indicate missing data.

12.1.6 Completion of forms

All paper forms must be completed and saved in the database. The study team member responsible for the entry of data into the database must ensure that all fields have been completed and that the form has been saved and marked as complete. If a form cannot be completed or data cannot be verified the form should be marked incomplete or unverified. Forms should only be marked unverified if PI or investigator review is required.

12.1.7 Missing or Incomplete data

Data may not be available to complete the forms for various reasons. Forms with missing data in fields or sections should be marked as INCOMPLETE in the study database. Indicate the reason for the missing data in the text field when available.

12.1.8 Incomplete or Illegible forms

If any section or an entire page of the forms cannot be completed (e.g., no parts have any responses), and it is unlikely that it will be completed, indicate NOT DONE/ND, NOT AVAILABLE/NA or NOT APPLICABLE/NAP, as appropriate. Do not leave forms incomplete or unused without explanation.

All form header information must be completed even though no data are recorded on the electronic form. If an electronic form can only be partially completed at the time of visit, but will be completed when the information becomes available, note this in the MISSING FORMS / INCOMPLETE FORMS field and follow the direction of the study coordinator and principal investigator.

13 Analysis Plan

Since the study is a pilot study to demonstrate feasibility of recruiting and training gout patients to utilize RheumPRO and IVR, a priori sample size calculations were not performed. We will summarize baseline characteristics of study participants as means with standard deviation (SD) for continuous and ordinal measures and number and percentage for categorical variables. All statistical analyses followed standard methods for a 2-by-2 crossover design. Preference and satisfaction surveys will use dichotomous questions and/or a Likert scale (range 0 to 10; very easy to very difficult). Differences between the RheumPRO and IVR approach will be evaluated using McNemar's test for dichotomous variables, paired t test for continuous variables, and nonparametric Wilcoxon signed rank test for ordinal variables. Qualitative questionnaire data for lack of response will be summarized as percentages. We will conduct sensitivity analyses with multiple imputations to examine the robustness of the reported results and the effects of missing data for both the as-treated and intent-to-treat populations. A two-sided alpha of 0.05 will be used to determine significance.

For comparisons of Fitbit® wear compliance data, descriptive statistics with proportions will be used. To study the changes in sleep and step counts on days when the participant reported a gout flare, we will use a mixed linear model to account for repeated observations and to adjust for potential confounders. The pattern of wear time for each participant over the course of the 6 month study will be examined descriptively using a heat map and colored as compliant wear with sleep days (red), compliant wear without sleep days (green), partial wear (blue) days, and no health tracker data (White) days. We will measure the association of flare with mean step counts and sleep duration collected from the wearable tracker device, comparing flare days to non-flare days. An alpha of 0.05 will be used to determine significance. All analyses will be performed with SAS (version 9.4, SAS, Cary, NC).

14 Study compliance

Protocol deviations will be tracked using the log below and notification of appropriate parties (UAB IRB) should take place following a deviation in the period specified by each party.

Protocol deviations include, but are not limited to, the following:

- Randomization of an ineligible participant
- Failure to obtain Informed Consent
- Entering a participant into another study
- Failure to keep IRB approval up to date
- Wrong treatment administered to participant

All deviations will be reported to the appropriate parties, including the Principal Investigator and to the IRB as soon as they are discovered. The study staff and research assistants will maintain the log of all protocol deviations

15 Quality Control and Standard Operating Procedures

All study procedures are to take place at UAB and UNMC and will do so in accordance with the Protocol.

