5.2 Participant Retention

To encourage adherence to the assigned study arm participants will be contacted 2 weeks after enrollment. Study coordinators will inquire about any challenges encountered (eg. technology issues—Fitbit not syncing, trouble logging in to the IRV/RheumPRO app). In addition, participant progress will be monitored on a weekly basis by UAB to ensure participants are completing their assigned weekly flare surveys. If any data from the participant is missing on the Fitbit, the study team will contact them to ensure they know how to charge their devices and are using it appropriately.

6 Eligibility criteria

No subject will be excluded based upon gender or race/ethnicity. All participants must meet the following criteria to be enrolled:

- \geq to 18 yrs. of age with Current physician diagnosed gout
- current hyperuricemia defined as serum urate level >6.8 mg/dl
 - Or if it has been >3 months since their last urate OR they have had an increase in ULT (or change in medication) in the past 3 months then a new urate of ≥ 6.0 must be documented to satisfy inclusion criteria.
- self-report of at least two gout flares in the previous 6 months

- Current smartphone user utilizing a FitBit compatible smart phone (with the ability to download RheumPRO from web link).

7 Informed Consent and HIPAA

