7.2 HIPAA Authorization

The privacy requirements, as outlined by The Health Insurance Portability & Accountability Act (HIPAA) to protect the participant's confidentiality, are met by reading through the consent form with the potential study participant before obtaining a signature. Additionally, the following HIPAA Specific requirements are met in the last section of the consent form:

The form contains language that satisfies the HIPAA requirements and outline the protection of health information utilized in the study. That participants are authorizing investigators, IRBs, research administrators, and others to share and disclose their Protected Health Information (PHI) for research purposes.

8 Study Supplies

Each participant will be supplied with a FitBit Charge HR wearable activity tracker. Fitbit will be supplied by UAB to 45 participants along with study binder.

9 Randomization

Randomization will occur by using a random number generator. Specifically, permuted block randomization will be used for balance between cross-over arms throughout the investigation. The study coordinator will maintain the master list and securely store the randomization files. Upon completion of the informed consent and screening CRFs, the RheumPRO application will automatically create a unique study ID. The study coordinator will initiate the randomization procedure after a subject has consented. If any concerns arise during the randomization procedures, the study coordinator will contact the study statistician.

10 Study Intervention

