The IVR system includes tailored scripting of Gout Flare and Patient Reported Outcome questions (with skip logic), recorded by a member of the research team. The system will automatically dial participants at a schedule time (eg. Monday 4 PM) and if no answer will attempt 2 more times at the same time over the following 2 days (eg. Tuesday 4 PM, Wednesday 4 PM). Participants will self-navigate through the questions using their telephone keypad. Participants can also call into the system to complete surveys if they experience a flare on a day they are not scheduled to receive a call. The IVR system will be programmed to call the patient weekly for 12 weeks to complete a weekly Gout Flare Survey. Consistent with the published gout flare self-report definition, gout flare ascertainment questions will include whether the recent flare is similar to past flares, the number of swollen joints and the number of warm joints. Pain at rest during the attack will be assessed on a 0-9 scale. Together, these questions attain 90% accuracy with physician-diagnosed gout. Further questions will include peak pain, timing of attack and duration of attack if completed. We will capture patient reported outcome measures (e.g. pain, fatigue, sleep) using instruments from the NIH PROMIS assessment center (<https://www.assessmentcenter.net/>). In addition IVR questionnaires at months 1, 3, and 6 will assess IVR ease of use, burden of use, willingness to continue use and disruption to daily activities. At enrollment the study coordinator will explain how the IVR works, planned survey schedule, and that participant -initiated calls to IVR are allowed.

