Participants randomized in Phase 1 to the RheumPRO application will complete the exact same Gout Flare Survey questions as the participants randomized to the IVR group, but will complete them using the RheumPRO application that will be downloaded on their smartphone. The RheumPRO application will be programmed to notify participants weekly for 26 12 weeks via a scheduled (eg. Monday 4 PM) “pop-up” to complete Gout Flare and Patient Reported Outcomes Surveys. Participants self-navigate through the survey questions using their smartphone. If participants do not complete the Gout Flare RheumPRO will generate 2 more “pop-ups” at the same time over the following 2 days (eg. Tuesday 4 PM, Wednesday 4 PM). Participants can also open the RheumPRO application on their smartphone and complete surveys or if they experience a flare on a day they are not scheduled to complete a survey. In addition, RheumPRO questionnaires at months 1, 3, and 6 will assess RheumPRO ease of use, burden of use, willingness to continue use and disruption to daily activities. At enrollment the study coordinator will explain how RheumPRO works, planned survey schedule, and that participant -initiated surveys in RheumPRO are allowed.

Phase 2:

At the conclusion of 12 weeks individuals will “crossover” to the opposite study arm and will continue in the study for an additional 12 weeks using the opposite technology to report their flare frequency/intensity (i.e., those randomized to IVR for the first phase will use the RheumPRO app in the second phase and vice-versa) completing the exact same Gout Flare and Patient Reported Outcome questions as were completed in Phase 1. Activities to be completed at each study visit are detailed below.

Figure 1. Study Workflow

[figure not shown]

Table 1. Study Visits and Evaluation

[figure not shown]
	1	2	3	4	5	6	7	8	9	10	11	12	13	14	15	16	17	18	19	20	21	22	23	24	
Informed Consent	X																								
Paper Screening	X																								
Paper Enrollment	X																								
IVR/RheumPRO Initial Flare Assessment	X																								
Patient- Weekly Flare Assessment*		X	X	X	X	X	X	X	X	X	X	X	X	X	X	X	X	X	X	X	X	X	X	X	X
2 week adherence call		X																							
1-month follow-up Assessment and phone check-in				X																					
3-month follow-up Assessment												X													
Crossover Study Visit†													X												
1-month follow-up Assessment and phone check-in																		X							

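### The RheumPRO versus IVR tests in Section 13 ignore period; period-adjusted crossover versions would cost almost nothing

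*Combined protocol and SAP*

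**What the plan says.** Section 13 (Analysis Plan) contains a general statement and a specific one. The general statement is "All statistical analyses followed standard methods for a 2-by-2 crossover design". The specific one assigns McNemar's test to dichotomous outcomes and a "paired t test for continuous variables, and nonparametric Wilcoxon signed rank test for ordinal variables". Significance is judged as follows: "A two-sided alpha of 0.05 will be used to determine significance". Because this is a feasibility pilot, "a priori sample size calculations were not performed".

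No period, sequence or carryover term is named for the mode comparison. The mixed linear model later in Section 13 is for steps and sleep on flare days, which is a different question.

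On design, Section 9 says "permuted block randomization will be used for balance between cross-over arms throughout the investigation". Section 10.1 says "IVR questionnaires at months 1, 3, and 6 will assess IVR ease of use" and, for the other mode, "RheumPRO questionnaires at months 1, 3, and 6 will assess RheumPRO ease of use". Section 5.2 says "participants will be contacted 2 weeks after enrollment"; Table 1 marks that adherence call once, in Phase 1.

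**The concern.** The usual reason for analysing a two-period crossover by sequence is that the second period may differ from the first whichever treatment is given. The three named tests look only at the RheumPRO minus IVR difference within each person and ignore which mode came first.

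The documents make a period difference plausible, although they give no size for it:

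- Each participant rates the first mode before trying the other, and rates the second after 12 weeks with the first.
- The 2-week adherence call belongs to Phase 1 only, although the 1-month check-in occurs in both phases.
- Response to weekly prompts may decline over about 24 weeks.

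Two things are at stake. With balanced sequences, the period difference enters the error term, so intervals are too wide and tests are conservative. If completers are unequal by sequence, part of the period effect is attributed to mode, in a direction that depends on which sequence loses more people. Permuted blocks balance the sequences at randomization, not among completers.

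**Working it through.** The plan states no sample size, power or effect size, so there is no figure of its own to reproduce.

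**Inputs.** Two-sided alpha of 0.05 is from Section 13. N = 45 is assumed from the Fitbit supply in Section 8; it is not a stated sample size. The completer splits, effect sizes and period effects are all assumptions.

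**Model, continuous outcome.** Let D be RheumPRO minus IVR for one person, with SD 1. Let π be the Phase 2 minus Phase 1 effect in the same units. D has mean τ + π in the IVR-first sequence (n1 people) and τ − π in the RheumPRO-first sequence (n2 people). Write n = n1 + n2.

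- Paired analysis: the estimate has mean τ + π(n1 − n2)/n. The expected sample variance of D is 1 + π² × 4·n1·n2/[n(n − 1)].
- Adjusted analysis: average the two sequence means of D. The estimate has mean τ, SE = ½√(1/n1 + 1/n2), and n − 2 degrees of freedom.

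**Balanced case, 23/22.** Here 4 × 23 × 22/(45 × 44) = 2024/1980 = 1.022, so the paired interval is wider by a factor of about √(1 + 1.022π²). Type I error and power (at τ = 0.43) are from simulation.

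| π (SD) | Bias, π/45 | Width ratio | Type I error, paired t | Power, paired t | Power, adjusted |
|---|---|---|---|---|---|
| 0.25 | 0.006 | 1.03 | 4.3% | 80% | about 81% |
| 0.5 | 0.011 | 1.12 | 2.8% | 76% | about 81% |
| 1.0 | 0.022 | 1.42 | 0.6% | 57% | about 81% |

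**Unequal completers.**

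- 22/18: bias is π × 4/40, or 0.025, 0.05 and 0.10 SD. Type I error stays below 5%.
- 22/14, a stress case: bias is π × 8/36, or 0.06, 0.11 and 0.22 SD. Type I error is 5.4%, 6.6% and between 7% and 8%.
- 14/22: the bias has the opposite sign. At π = 0.5, paired t power falls to 37%, against 68% adjusted.

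**Ordinal 0–10 item, 23/22.** Assume an SD of the difference of about 2 points and a true difference of about 0.9 point. Signed rank power is 82%, 76% and 51% at period shifts of 0.5, 1 and 2 points. The rank-sum test by sequence on period differences holds 83–84%.

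**Dichotomous outcome.** Assume a random-intercept logistic model with mode log-odds 1.5.

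- At 23/22, power for McNemar against the Mainland-Gart chi-square is 82/82%, 81/80% and 70/66% at period log-odds of −0.5, −1 and −2. There is no gain when sequences are balanced.
- At log-odds −1, the pooled risk difference is 0.23 (22/14) or 0.31 (14/22), against 0.27 when the two sequences are averaged.
- Under a separate set of assumptions with a period effect at 23/22, the Prescott test, which also uses the concordant pairs, had 85% power against 77% for McNemar.

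**Cost when there is no period effect.** At 23/22 the adjusted SE is ½√(1/23 + 1/22) = 0.1491, against √(1/45) = 0.1491 (ratio 1.0002). Critical t moves from 2.0154 (44 df) to 2.0167 (43 df), so the interval widens by 0.09%. Simulated power is:

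| Outcome | Split | Adjusted | Unadjusted |
|---|---|---|---|
| Continuous | 23/22 | 80.5% | 80.6% |
| Ordinal | 23/22 | 83.5% | 84.5% |
| Continuous | 22/14 | 69% | 71% |
| Ordinal | 22/14 | 71% | 75% |

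**The case against.** - **The general sentence may already cover this.** Period adjustment is commonly part of 2-by-2 crossover analysis. That supports the intent, but the tests then named do not adjust, and Section 19 ties the first publication to analysis as the protocol stipulates. At the least the two sentences need reconciling.
- **Imputation could restore balance.** Section 13 plans multiple-imputation sensitivity analyses for the as-treated and intent-to-treat populations. If every randomized participant were imputed, the split would return to roughly that at randomization. This partly answers the bias argument, but it is a sensitivity analysis with no stated model, and it does not recover the precision lost to the period effect.
- **The harm depends on assumed sizes.** This stands. At 0.25 SD the loss is about 1 point of power, and inflated type I error needs an imbalance as marked as 22/14. The study is a pilot with no power target.
- **The binary case is weak.** This largely stands. Mainland-Gart gives no gain with balanced sequences, and its exact form costs about 4 points against exact McNemar (72.2% against 76.4%). Its value is protection under imbalance. The performance of a logistic mixed model in a sample this small was not examined.
- **The mechanisms may be carryover.** If experience with one mode shifts later ratings differently from experience with the other, a period term will not remove that. This is correct, and it limits what the change can achieve.

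**Conclusion.** The concern holds. The three named tests have no period term, nothing else in the document supplies one for the mode comparison, and the general reference to crossover methods does not change what the named tests do.

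The consequence is modest. While sequences stay near-equal, bias is negligible (at most 0.02 SD in the cases examined). The harm is lost precision for continuous and ordinal outcomes, small at a period effect of 0.25 SD and substantial only near 1.0 SD. Material bias needs both a period effect and unequal completion by sequence. For dichotomous outcomes the case rests mainly on that protection.

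All sizes rest on N = 45 and on assumed period effects and splits. It should be fixed because the change is cheap and Section 13 tests mode differences at the 5% level; it does not invalidate the pilot.

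**What to change.** In Section 13, make the main mode comparison period-adjusted:

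- **Continuous:** a linear mixed model with mode, period and sequence as fixed effects and participant as random, or a two-sample t test by sequence on within-participant period differences.
- **Ordinal 0–10 items:** a Wilcoxon rank-sum test by sequence on period differences.
- **Dichotomous:** a logistic mixed model with mode and period, or a period-adjusted test (Mainland-Gart or Prescott), with the choice and the exact or asymptotic form stated in advance.

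Report each mode difference with a 95% confidence interval, and tabulate summaries by sequence and period so that a period effect can be seen. State that the period term does not address carryover. Only the mixed models keep Phase 1 data from participants who do not cross over; the other tests need both phases, as the current ones do.

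The cost is a wording change, a few lines of SAS and, for the t test, one degree of freedom. If there is no period effect and completers are as unequal as 22/14, power falls by about 2 points (continuous) to 4 points (ordinal).

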10.2.2 Visits 2-12

- Visits 2-12 will be completed by participant using IVR or RheumPRO application
- Participants will receive notification the day of, 24 hours, and 48 hours later
 - IVR will call participant at designated time to complete
 - RheumPRO will send push notifications participants to complete survey

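### Does the Fitbit analysis need a written rule for turning flare reports into flare days?

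*Combined protocol and SAP*

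**What the plan says.** Section 13 (Analysis Plan) words the Fitbit exposure in two ways. One is the aim "To study the changes in sleep and step counts on days when the participant reported a gout flare"; the other is "comparing flare days to non-flare days". Neither term is defined further.

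Section 10.1 (Overview) describes a weekly flare survey that asks, among other things, "whether the recent flare is similar to past flares". It continues: "Further questions will include peak pain, timing of attack and duration of attack if completed". Participants using the app "will complete the exact same Gout Flare Survey questions as the participants randomized to the IVR group".

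On the timing of scheduled reports, Section 10.2.2 says: "Participants will receive notification the day of, 24 hours, and 48 hours later". Between surveys, Section 10.2.5 says that "participants have the ability to enter flare information on an ad hoc basis". For the app's interval form, Section 10.2.5.1 instructs staff: "Stress to them the importance of completing this form ONLY when they feel they are having a gout flare".

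**The concern.** The aim stated in Section 13 can be read literally as the day the report was made. A weekly survey about a recent flare, which asks duration only for a finished attack, will sometimes be answered after the attack has ended. A day without flare would then be coded as a flare day, and the real flare days would sit in the comparison group. One attack can also be reported twice, ad hoc and in the weekly survey, and no section says such reports are merged. Two analysts could both follow Section 13 and obtain different step and sleep differences, each tested at an alpha of 0.05.

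**Working it through.** The plan gives no effect size, flare duration or share of ad hoc reports, so there is no figure of its own to reproduce.

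**Inputs.** Follow-up is 12 + 12 weeks = 168 days (Section 10.1). I assume k = 2 flares per participant; the only anchor is the entry requirement of at least two in the previous 6 months (Section 6). Durations d of 3, 5 and 7 days and onset uniform over the week are also assumptions.

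**Formula.** If the flare effect is constant over the attack, and coding is unrelated to steps or sleep given true flare status, the share of the true difference retained is

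R = P(true flare day | coded flare) − P(true flare day | coded non-flare) = t/c − k(d − t)/(168 − kc),

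where each flare yields c coded days, t of them true flare days.

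**Report-day coding.** Example for weekly reports and d = 3, with c = 1 and t = 3/7: R = 0.429 − 2(3 − 3/7)/166 = 0.429 − 0.031 = 0.398.

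| How flares are reported | c | t | d = 3 | d = 5 | d = 7 |
|---|---|---|---|---|---|
| Weekly, first prompt | 1 | d/7 | 40% | 66% | 93% |
| Weekly, repeated at the next survey if ongoing | 1 + (d−1)/7 | d/7 | 30% | 40% | 47% |
| Once, at onset | 1 | 1 | 98% | 95% | 93% |
| At onset and at the next weekly survey | 13/7 | 1 + (d−1)/7 | 67% | 80% | 94% |

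With k = 4, the first row becomes 37%, 61% and 85%.

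**Reminder delay.** Suppose the survey is answered 0, 1 or 2 days late, equally often, and covers flares up to the actual answer. For onset 0 to 6 days after the scheduled day, the chance that the report falls within the attack is:

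- d = 3: 1, 2/3, 1/3, 0, 0, 1/3, 2/3; sum 3, so t = 3/7
- d = 5: 1, 2/3, 1/3, 1/3, 2/3, 1, 1; sum 5, so t = 5/7
- d = 7: 1, 7/9, 7/9, 1, 1, 1, 1; sum 59/9, so t = 0.937

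R is then 40%, 66% and 0.937 − 2(7 − 0.937)/166 = 86%. Reminders therefore cost nothing at 3 and 5 days and about 6 points at 7 days.

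**Onset-to-end coding.** Suppose reported onset is off by −e, 0 or +e days, equally often, and duration is exact. Then c = d and t = d − 2e/3.

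| Onset error | d = 3 | d = 5 | d = 7 |
|---|---|---|---|
| e = 0 | 100% | 100% | 100% |
| e = 1 | 77% | 86% | 90% |
| e = 2 | 54% | 72% | 79% |

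Any error in duration would change these values.

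**Direction.** Drop the constant effect. Take k = 4 and d = 5, with the first two days at 1.5 times the flare average, so that the other three are at (5 − 3)/3 = 2/3.

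- All reported at onset: 1.5 − 4(5 − 1.5)/164 = 1.41.
- All weekly: the mean effect on coded days is (2 × 1.5 + 3 × 2/3)/7 = 0.714, and 0.714 − 4(5 − 0.714)/164 = 0.61.
- Half and half: the mean is 1.107, and 1.107 − 4(5 − 1.107)/164 = 1.01.

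Simulation over 5-, 7- and 10-day flares gave 1.02 to 1.42 when half or more of reports were made at onset. Attenuation toward zero is thus usual but not assured.

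**The case for a change.** The case for writing a rule is reasonable. Section 10.1 says the Fitbit data are explored to see whether prompts could be more timely, and that depends on which day a flare began. Section 13 attaches a significance level. Section 19 requires the first publication to rest on data analysed as the protocol stipulates, and here the stipulation is incomplete. The remedy would be mostly wording, since both modes ask timing and duration.

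What stands is that the definition is missing. So are a rule for merging repeat reports of one attack and a rule for which night's sleep belongs to a flare day.

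What does not stand is that a particular rule should replace the present text:

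- **The gain is not assured.** With 2-day onset errors, onset-to-end coding (54%, 72%, 79%) does worse at all three durations than coding the onset report plus the next weekly report (67%, 80%, 94%). With 1-day errors it is still worse at 7 days (90% against 94%). It does clearly better than weekly-only coding of short flares.
- **It may not be workable as stated.** The questionnaire is not in the documents, so whether the timing item records an onset date is unknown. The survey's recall window is not given either, so days covered by no report cannot be identified.
- **Harm needs an unfavourable choice.** It arises if the analyst takes the report day and ignores the attack dates already collected.

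**Conclusion.** No change to the plan is needed. Section 13 leaves a flare day undefined. Its comparison of flare with non-flare days, together with the timing and duration items, gives analysts what they need to choose a sensible coding once they see the questionnaire, and to report it with the result.

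Across the two-flare report-day settings tabulated above, the share retained runs from 30% to 98%. It can exceed 100% when the effect peaks early and many flares are reported at onset. All of this rests on assumed durations, flare counts and reporting habits, so it shows sensitivity and does not estimate a bias in this trial.

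The stake is small. The Fitbit association is exploratory, the trial is a feasibility pilot without a sample size calculation, and no comparison of RheumPRO with IVR uses flare days. The conclusion would be different if the plan had fixed the report day as the exposure and set aside the attack dates; it does not do so clearly.
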